11.4 Efficacy Assessments

Statistical analysis of efficacy assessments includes changes in the EASI, IGA, and PP-NRS. Methods are described in detail in the SAP.

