#### 3. Analysis Population

The statistical analysis sets involved in this study are as follows:

**Enrolled Population:** including all subjects who sign informed consent form and are successfully screened.

**Safety Analysis Set:** including all the subjects who received at least one dose of the study drug. This analysis set will be used for analysis of safety endpoint.

Efficacy Analysis Set: including all the subjects who received at least one dose of the study drug and have undergone at least one post-baseline efficacy assessment. This analysis set will be used for analysis of efficacy endpoint.

Per protocol analysis set: a subset of efficacy analysis set of patients without any importance protocol violation, as defined by the sponsor prior to the data base locked (adhere to ICH E3 guidance) Important protocol deviations are a subset of protocol deviations that might significantly affect the completeness, accuracy, and/or reliability of the study data or that might significantly affect a subject's rights, safety, or well-being. For example, important protocol deviations might include enrolling subjects in violation of key eligibility criteria designed to ensure a specific subject population or failing to collect data necessary to interpret primary endpoints, as this may compromise the scientific value of the trial.

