#### 4.1.4 Visit Window

The nominal visit as defined in protocol and recorded on the Case Report Form (CRF) will be used in the statistical analyses unless other specified. Regarding efficacy endpoints, the analysis visit during follow-up period will be dynamically derived. For instance, if the subject finished the last dosing visit at Week 14, the first follow-up visit (i.e. FU1) will be set as the first visit after Week 14 (i.e. Week16) and subsequent follow-up visits will be derived accordingly as Week18, Week20, Week 22, Week24, and Week 26. Unscheduled data will not be windowed into planned analysis visits for summary tables but will be included in overall post-baseline summaries, such as worst or last values.

In addition, unscheduled data will be listed and may be plotted in figures based on study days.

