#### 4.1.5 Missing Data

Unless otherwise specified, missing data will be treated as missing, ie, no special handling will be performed. For demographic and baseline characteristics, each variable will be analyzed and/or summarized using the available data. Details of efficacy and safety data handling will be documented in efficacy and safety analyses section.

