#### 4.7 Efficacy Analysis

Efficacy analysis will be summarized in efficacy analysis set. As a sensitivity analysis, the per protocol population will also be assessed.

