#### 4.7.1 Eczema Area and Severity Index (EASI)

The EASI score is a composite index that measures the severity of AD based on the average intensity of four clinical signs (erythema, edema/papulation, excoriations, and lichenification) at four body areas (head, neck, upper extremities, and trunk and lower extremities), and the percentage of affected area for each of the four body areas.

The baseline for EASI is defined as the score measured prior to dosing on Day 1.

Measured values, changes from baseline and percent change from baseline in EASI score will be summarized descriptively on scheduled visit.

The primary efficacy endpoint is the proportion of subjects with EASI75 (a 75% reduction in the EASI score) at 2 weeks after last dose at Week 24. The exploratory endpoints include the proportion of subjects achieving EASI90 at Weeks 26 (2 weeks after last dose at Week 24), the proportion of patients with EASI50 at Week 26 (2 weeks after last dose at Week 24). The corresponding 95% two-sided confidence intervals (CIs) will be calculated using the exact binomial distribution and presented for EASI75, EASI90, and EASI50.

For primary analysis, the percent change from baseline in EASI score, EASI50, EASI75, EASI90 in the EASI score will be calculated with observed data. If the subject has missing value for EASI at scheduled visit, the subject will be excluded from the calculation of proportion at specify visit.

Mean (±standard deviation) of the percent change from baseline in EASI score with observed data will be plotted at scheduled visit.

For sensitivity analysis, the missing value will also be imputed with last observation carried forward (LOCF) method. The imputed data for the percent change from baseline in EASI score will be summarized descriptively on scheduled visit. The proportion of subjects with EASI50, EASI75 and EASI90 at 2 weeks after last dose at Week 26 will also be calculated with imputed data.

A listing of all EASI score will be provided by subject number.

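### The primary EASI75 proportion drops every patient without a Week 26 EASI and has no rule for scores taken after a switch to another AD treatment, so it can overstate response to monotherapy.

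*SAP*

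**What the plan says.** SAP 4.7 sets the population: "Efficacy analysis will be summarized in efficacy analysis set". SAP 3 defines that set as patients who had at least one dose and "have undergone at least one post-baseline efficacy assessment".

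SAP 4.7.1 then fixes which scores are used: "For primary analysis, the percent change from baseline in EASI score, EASI50, EASI75, EASI90 in the EASI score will be calculated with observed data". The rule for the denominator comes next: "If the subject has missing value for EASI at scheduled visit, the subject will be excluded from the calculation of proportion at specify visit". SAP 4.7.2 repeats the exclusion rule for IGA 0/1, and SAP 4.7.4 carries it to facial IGA. The sensitivity analyses are LOCF (SAP 4.7.1) and the per-protocol set (SAP 4.7).

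On visits, SAP 4.1.4 takes a patient last dosed at Week 14 and maps FU1 to Week 16; "subsequent follow-up visits will be derived accordingly as Week18, Week20, Week 22, Week24, and Week 26". Unscheduled assessments cannot fill a gap at Week 26: "Unscheduled data will not be windowed into planned analysis visits for summary tables but will be included in overall post-baseline summaries".

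On data after a change of treatment, Protocol 7.11 makes starting a new AD therapy a reason to stop study drug permanently, and asks for further follow-up assessments after stopping. Protocol 11.4 leaves the efficacy analysis to the SAP ("Methods are described in detail in the SAP"). SAP 4.1.5 passes the matter on again: "Details of efficacy and safety data handling will be documented in efficacy and safety analyses section". Sections 4.7 to 4.7.4 contain no rule for scores recorded after a switch.

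**The concern.** The synopsis objective is efficacy as monotherapy. The trial is unblinded and has no control arm, so this one proportion is the headline efficacy result, and Protocol 5.4 says the findings will be used to design the Phase 2b study.

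Two features can push it upward. First, a patient who stops early and has no Week 26 score leaves the denominator instead of counting as not having responded. If patients stop because the drug is not working, the remaining group is selected for success. Second, a patient who fails on BSI-045B, starts another AD treatment and improves can be counted as a responder to BSI-045B, because the visit mapping can place that later score at Week 26.

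The planned sensitivity analyses do not settle this. LOCF helps in part: EASI is collected at early withdrawal, so a failing last score is carried forward as a failure. It can equally carry forward an on-drug or post-switch response. Its time point is also misstated, because it refers to a last dose at Week 26 and no dose is given then. The per-protocol analysis removes more patients. No planned analysis counts patients who are missing at Week 26, or who have switched, as non-responders.

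**Working it through.** **The plan's own figure.** Protocol 11.1 and SAP 2.3 give a maximum one-sided 95% interval width of 21% at n = 20 and 19% at n = 24. The largest distance from x/n to the exact one-sided bound is 20.8% (n = 20) and 18.8% (n = 24), so the figures reproduce. They assume that all 20 or 24 patients are in the denominator. With 18, 16 or 14 observed, the width is 22.1%, 23.6% or 25.4%.

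**Who has no scheduled Week 26 visit.** Doses fall at Weeks 1, 2, 3, 4 and then every two weeks from 6 to 24: 4 + 10 = 14 doses, the fifth at Week 6. Protocol 7.3 replaces only patients with fewer than 5 doses. FU6 is the last-dose week + 12 (Protocol Table 2):

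| Last dose | Doses | FU6 |
|---|---|---|
| Week 6 | 5 | Week 18 |
| Week 8 | 6 | Week 20 |
| Week 10 | 7 | Week 22 |
| Week 12 | 8 | Week 24 |
| Week 14 | 9 | Week 26 |

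The visit windows do not close the gap. In days from the nominal Week 24 visit, the latest FU6 for a Week 12 stopper is +3 (dose) + 3 (FU6) = +6. The earliest Week 26 visit is −3 + 14 − 3 = +8, which is 2 days later. By contrast, a patient last dosed at Weeks 14 to 22 can have a Week 26 score 12 to 4 weeks off drug, possibly on another AD treatment, and counts as observed.

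**Effect of exclusion.** The documents give no dropout, switch or response rate, so what follows is assumption. With N dosed, r observed responders and m missing, the plan reports r/(N − m), non-responder imputation gives r/N, and the upper bound is (r + m)/N. For N = 20 and r = 8:

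| m | As written | Non-responder | Gap (points) |
|---|---|---|---|
| 0 | 8/20 = 40.0% | 40.0% | 0 |
| 1 | 8/19 = 42.1% | 40.0% | 2.1 |
| 2 | 8/18 = 44.4% | 40.0% | 4.4 |
| 4 | 8/16 = 50.0% | 40.0% | 10.0 |

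Exact two-sided 95% intervals are 24.7 to 75.3 for 8/16 and 19.1 to 63.9 for 8/20. With m = 4 the upper bound is 12/20 = 60%. LOCF gives 40, 45, 50, 55 or 60% as 0 to 4 of the missing patients carry forward a response.

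These gaps equal bias only if no excluded patient would have responded. In general, overstatement = share missing × (response among observed − response among missing). With 20% missing and 50% response among the observed, it is 10 points if none of the missing would respond, 5 if 25% would, 0 if 50% would and −5 if 75% would.

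**Effect of replacement.** Take 20 patients all observed, 8 responders, and 4 more replaced before their fifth dose. The plan reports 8/20 = 40.0%. Over all dosed patients it is 8/24 = 33.3% (15.6 to 55.3), a gap of 6.7 points. The same holds over the Efficacy Analysis Set if all four had a post-baseline efficacy assessment.

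**Effect of a switch.** With no missing data, each responder counted after a switch adds 1/20 = 5.0 points or 1/24 = 4.2 points.

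**The case against.** The observed-case rule is explicit, prespecified and paired with two sensitivity analyses. Non-responder imputation swaps one untestable assumption for another. The direction of any bias is unknown, no hypothesis test is planned (SAP 4.1.1), and no success threshold is stated. With 1 or 2 patients missing, the gap is small beside a stated precision of 19 to 21 points. The planned EASI, medication and disposition listings let a reader recompute the rate. Replacement is deliberate, since the protocol aims for 20 to 24 evaluable patients. These points stand, and they limit how much the issue matters.

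It can also be said that switchers are not wholly unaddressed. Protocol 9.4 permits no rescue medication and Protocol 9.5 restricts certain therapies. Protocol 7.13 and 11.3.2 allow individual patients to be left out of an analysis, and a switch might be judged an important deviation under SAP 3. But the first two govern conduct, and the others are discretionary exclusions that would shrink the denominator further. None says whether a post-switch EASI is used, set to missing or counted as failure.

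Listings permit reconstruction afterwards; they do not prespecify the headline number. The sensitivity analyses have the gaps described above.

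**Conclusion.** The concern holds. As written, the primary proportion is not calculated over the SAP's declared efficacy set. The schedule guarantees that some unreplaced early stoppers cannot contribute, and post-switch scores can count as monotherapy responses.

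The size cannot be taken from the documents. Under the stated assumptions the difference from non-responder imputation is 0 to 10 points for 0 to 4 missing of 20, plus about 4 to 5 points for each responder counted after a switch. The rate overstates response only if excluded patients would have done worse than those observed, or if switchers owe their response to the new treatment. In a proof-of-concept study with no formal test this should be fixed, but it does not invalidate the trial.

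**What to change.** In SAP 4.7.1:

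- Make non-responder imputation the primary EASI75 analysis, over the full Efficacy Analysis Set or all dosed patients, and say which.
- Count as non-response a missing Week 26 EASI, or new or prohibited AD therapy started before the Week 26 assessment. List the therapies that qualify and say how partial start dates are handled, since Appendix 1 moves them to the start of the month or year.
- Use off-drug Week 26 scores without a switch as observed.
- Apply the same rule to EASI50, EASI90, IGA 0/1 and facial IGA.
- Keep observed-case, LOCF and per-protocol as sensitivity analyses, and correct the LOCF time point to Week 26, two weeks after the Week 24 dose.
- Report the numbers missing, off drug and post-switch at Week 26.

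The cost is SAP text and programming; no new data are needed. The reported rate will be lower or unchanged. It will understate response if some missing patients were true responders or stopped for unrelated reasons (up to 5 points each at N = 20). A Week 12 stopper still responding at FU6 (Week 24) counts as a failure, while a Week 14 stopper with the same FU6 result (Week 26) does not. The retained LOCF analysis will show that difference.

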# 4.7.2 Investigator's Global Assessment of Disease Severity (IGA)

The IGA requires the investigator to rate the severity of AD on a scale from 0 (clear) to 4 (severe).

The baseline for IGA is defined as the score measured on Day 1.

Proportion of subjects achieving an IGA response (IGA = 0 [clear] or IGA = 1 [almost clear] on a scale of 0–4, where 4 represents severe atopic dermatitis) at 2 weeks after last dose at Week 24 with observed data will be presented. If the subject has missing value for IGA at scheduled visit, the subject will be excluded from the calculation of proportion at specify visit. The corresponding 95% two-sided confidence intervals (CI), calculated using the exact binomial distribution, will also be presented.

A listing of all IGA result will be provided by subject number.

# 4.7.3 Peak Pruritus Numerical Rating Scale (PP-NRS)

The assessment tool for itching is the PP-NRS, on which the subject rates the maximum severity of the itch from AD on a scale from 0 (no itch) to 10 (worst itch imaginable) over a 24-hour period. The baseline PP-NRS score is based on the average of daily PP-

NRS scores for the 7 days immediately preceding Day 1. In order to calculate an average for the score, the subject must have completed the diary for a minimum of 4 days during the previous 7 days.

Measured values, changes from baseline and percent change from baseline in PP-NRS score will be summarized descriptively at 2 weeks after last dose at Week 24.

The PP-NRS score at Week 26 (2 weeks after last dose at Week 24) is based on the average of the first consecutively 7 days recorded on visit of FU2, as the PP-NRS score for a treatment cycle will be collected at the next visit.

Mean (±standard deviation) of percent change from baseline of PP-NRS score with observed data will be plotted at scheduled visit.

A listing of all PP-NRS score will be provided by subject number.

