- 6. Clinical laboratory assessments:
- Hematology: Hemoglobin, hematocrit, WBC count and differential, RBC count and indices, platelet count
- *Chemistry*: Sodium, potassium, chloride, bicarbonate, calcium, phosphorus, magnesium, glucose, BUN, creatinine, uric acid, ALT, AST, GGT, alkaline phosphatase, total protein, albumin, globulin, total bilirubin, LDH, total cholesterol, triglycerides
- Coagulation: PT, aPTT, fibrinogen, INR
- *Urinalysis*: Protein, glucose, ketones, occult blood, urobilinogen, urine sediment microscopy (if other parameters abnormal)
- 7. For patients requiring washout, clinical laboratory assessments and urine toxicology test should be repeated to make sure the tests are conducted within 14 days prior to W1D1.
- 8. Urine toxicology: Urine toxicology testing is optional. If the PI has no concerns about the use of illicit drugs by a patient, testing for drugs of abuse is not required. If the PI has concerns, a negative urine/blood result for drugs of abuse is required at Screening. Screening assessment on urine toxicology should be repeated if they are performed ≥14 days before W1D1.
- 9. Virology screening: HbsAg, anti-HCV, HIV.
- 10. All patients should be monitored in the study sites for at least 30 mins after each dose to observe body reactions, including injection site reactions. Any injection site reactions observed after each site visit should be reported to the Investigators by the patients.
- 11. Efficacy assessments: EASI, IGA, facial IGA and PP-NRS. For PP-NRS: Patients will complete the PP-NRS daily in a patient diary beginning on Day -8, throughout the last study visit, and at the time of early withdrawal from the study, and scores for each timepoint will be the average of scores over the past 7 days. In order to calculate an average for the score, the patient must have completed the diary for a minimum of 4 days during the previous 7 days. Investigator should also assess Facial IGA. For the assessment of conjunctivitis, diagnosis history with severity will be recorded at screening, and at every visit during the treatment period, all patients will be asked if they had been diagnosed as conjunctivitis since last visit. Conjunctivitis severity grade includes: 0 = no conjunctivitis; 1 = mild conjunctivitis; 2 = moderate conjunctivitis requiring treatment; 3 = severe conjunctivitis that may require an ophthalmic exam. Investigators should also check the patients' eyes and record any findings.

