- 12. PK blood sample collection: Within 1 h before each dose during the Treatment Period.
- 13. Immunogenicity blood sampling: Blood samples are to be collected at W1D1, W2, W3, W4, W8, W12, W16, W20, and W24 within 1 h before each dose during the Treatment Period.
- 14. Biomarker blood sample collection: Assessments are TARC/CCL-17, periostin, and IgE. Samples are to be obtained at W1D1, W2, W3, W4, W8, W12, W16, W20, and W24 within 1 h before each dose during the Treatment Period.

V4.0_8 Jul 2024 Page 19 of 68

Table 2. Follow-up, End of Study, and Early Withdrawal

	Follow-up Period						
Study Procedure	FU1 (2 weeks after last dose±3d)	FU2 (4 weeks after last dose±3d)	FU3 (6 weeks after last dose±3d)	FU4 (8 weeks after last dose±3d)	FU5 (10 weeks after last dose±3d)	FU6 (12 weeks after last dose±3d)	(+7d)
12-lead ECG ²	X						X
Vital signs ²	X	X	X	X	X	X	X
Physical examination (system driven)		X		X		X	X
Clinical labs ^{2,3}		X		X		X	X
Blood pregnancy test (females of childbearing potential only)							X
Urine pregnancy testing (females of childbearing potential only)		X		X		X	
Efficacy assessments and patient diary (EASI, IGA, facial IGA, PP-NRS) ⁴	X	X	X	X	X	X	X
PK sample collection ^{2,5}	X	X	X	X	X	X	X
Immunogenicity sample collection ^{2,6}		X		X		X	X
PD Biomarker sample collection ^{2,7}		X		X		X	X
Assess concomitant medications	X						
Monitor and document AEs							

AE = adverse event; ALT = alanine aminotransferase; aPTT = activated partial thromboplastin time; AST = aspartate aminotransferase; CCL-17 = C-C chemokine ligand 17; EASI = Eczema and Severity Index; ECG = electrocardiography; GGT = gamma glutamyl transferase; IGA = Investigator's Global Assessment; IgE = immunoglobulin E; IL = interleukin; INR = international normalized ratio; LDH = lactate dehydrogenase; PD = pharmacodynamic; PK = pharmacokinetic; PP-NRS = Peak Pruritus Numerical Rating Scale; PT = prothrombin time; RBC = red blood cell; TARC = thymus and activation regulated chemokine; W = week; WBC = white blood cell

- 1. Early withdrawal: Early withdrawal assessments must be completed within 7 days after the last treatment with BSI-045B or within 7 days after the patient's decision to discontinue study treatment, whichever occurs first. When medically feasible, the Medical Monitor should be consulted prior to study drug discontinuation.

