- 2. Order of assessments: When collecting PK, immunogenicity, biomarker, and clinical laboratory samples, vital signs, and/or ECG assessments are scheduled to occur at the same time point, ECG and vital signs testing will be performed prior to blood collections. The preferred order of assessments is: 1) ECG, 2) vital signs, 3) PK, immunogenicity, and PD/biomarker sampling, 4) clinical laboratory sampling.

V4.0_8 Jul 2024 Page 20 of 68

- 3. Clinical laboratory assessments:
- Hematology: Hemoglobin, hematocrit, WBC count and differential, RBC count and indices, platelet count
- *Chemistry:* Sodium, potassium, chloride, bicarbonate, calcium, phosphorus, magnesium, glucose, BUN, creatinine, uric acid, ALT, AST, GGT, alkaline phosphatase, total protein, albumin, globulin, total bilirubin, LDH, total cholesterol, triglycerides, CK, CK isoenzymes
- Coagulation: PT, aPTT, fibrinogen, INR
- Urinalysis: Protein, glucose, ketones, occult blood, urobilinogen, urine sediment microscopy (if other parameters abnormal)
- 4. Efficacy assessments: EASI, IGA, facial IGA, and PP-NRS. Patients will complete the PP-NRS daily throughout the last study visit, and at the time of early withdrawal from the study, and scores for each timepoint will be the average of scores over the past 7 days. In order to calculate an average for the score, the patient must have completed the diary for a minimum of 4 days during the previous 7 days. Investigator should also assess Facial IGA.
- 5. PK blood sample collection: At each visit during the Follow-up Period, and at the time of early withdrawal from the study drug.
- 6. Immunogenicity blood sampling: Blood samples are to be collected at FU2, FU4, and FU6 during the Follow-up Period, and at the time of early withdrawal from the study drug.
- 7. Biomarker blood sample collection: Assessments are TARC/CCL-17, periostin, and IgE. Samples are to be obtained at FU2, FU4, and FU6 during the Follow-up Period, and at the time of early withdrawal from the study drug.

V4.0 8 Jul 2024 Page 21 of 68

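### The SAP scores Week 26 itch (PP-NRS) from diary days recorded at FU2, about a week later than the look-back week the protocol defines

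*SAP*

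**What the plan says.** Percent change in PP-NRS at Week 26, two weeks after the Week 24 dose, is an exploratory endpoint (Protocol Table 5; SAP Table 1).

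**Protocol.** Footnote 11 to Table 1 and footnote 4 to Table 2 carry the same rule: "scores for each timepoint will be the average of scores over the past 7 days", with at least 4 of the previous 7 diary days completed. Table 2 sets the visits: "FU1 (2 weeks after last dose±3d" and "FU2 (4 weeks after last dose±3d". FU1 is therefore the Week 26 visit, and Table 2 schedules the diary and PP-NRS at FU1 itself. The diary continues in follow-up: "Patients will complete the PP-NRS daily throughout the last study visit".

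**SAP 4.7.3.** Baseline looks back, using "scores for the 7 days immediately preceding Day 1". The completeness rule also looks back: the patient must have "completed the diary for a minimum of 4 days during the previous 7 days". The Week 26 score, however, "is based on the average of the first consecutively 7 days recorded on visit of FU2". The reason given is "as the PP-NRS score for a treatment cycle will be collected at the next visit". The SAP does not say that this departs from the protocol.

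**The concern.** The two documents appear to assign different diary days to the same endpoint. If a cycle's scores are collected at the next visit, the FU2 record covers the time from FU1 to FU2, and its first seven days start at or just after the Week 26 visit. The protocol's seven days end just before that visit.

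Four things follow if the SAP is programmed as written:

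- The reported Week 26 itch score is not the one the protocol defines, and a reader of the protocol would not know.
- The percent change sets a look-forward value against a look-back baseline.
- Itch would not cover the week leading up to the Week 26 EASI and IGA assessments.
- The rule is tied to a collection visit and not to dates, so the week scored could depend on which visits a patient attended.

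**Working it through.** There is no plan figure to reproduce. The check is day arithmetic.

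**Inputs.** Take the Week 24 dose as day 0. This is study Day 1 + 23 × 7 = 162, with W1D1 as Day 1. From Protocol Table 2, FU1 is on day v, nominally 14 (Day 176), range 11–17. FU2 is nominally day 28 (Day 190), range 25–31.

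**Protocol window.** The past 7 days before FU1 are v−7 to v−1, nominally days 7–13.

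**SAP window, FU1 attended and its diary collected there.** The FU2 record then starts at FU1 or the day after, so the window is v to v+6 or v+1 to v+7. The time between the visits is at least 25 − 17 = 8 days and at most 31 − 11 = 20 days, so seven days always fit.

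| Case (nominal v = 14) | Protocol days | SAP days | Midpoint shift | Shared days |
|---|---|---|---|---|
| FU2 record starts on FU1 day | 7–13 | 14–20 | 17 − 10 = 7 | 0 |
| FU2 record starts the day after | 7–13 | 15–21 | 18 − 10 = 8 | 0 |
| Visit day counted in both windows | 8–14 | 14–20 | 17 − 11 = 6 | 1 |
| FU1 missed, record starts on dose day | 7–13 | 0–6 | 3 − 10 = −7 | 0 |
| FU1 missed, record starts the day after | 7–13 | 1–7 | 4 − 10 = −6 | 1 |

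The first three rows do not depend on when FU1 falls, because both windows are anchored on the actual FU1 date. With v = 11 the windows are days 4–10 and 11–17; with v = 17 they are days 10–16 and 17–23. There is no overlap in either case.

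The last two rows assume that a diary running from Week 24 is collected at FU2 when FU1 is missed. The nominal FU1 date (day 14) is kept as the protocol reference.

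**Does the collection reason require the later week?** No. The diary is daily. By the same logic, the record collected at FU1 covers Week 24 to FU1, which contains days 7–13.

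**FU1 attended, FU2 missed.** The Week 26 score could be lost although the days before FU1 were recorded. With 20 to 24 evaluable patients, one such patient is 1/20 = 5% to 1/24 = 4.2% of the sample.

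**Early stoppers.** SAP 4.1.4 relabels follow-up visits for efficacy. In its own example (last dosing visit Week 14), FU1 becomes Week 16 and the later visits are Weeks 18, 20, 22, 24 and 26. FU2 is then Week 18, and Week 26 is FU6. The FU2 sentence in 4.7.3 names the wrong visit for that patient.

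**The case against.** The strongest reply is that the SAP's choice is coherent and was within its remit. Counting from W1D1, calendar Week 26 is Days 176–182, which is exactly days 14–20 after the Week 24 dose. The SAP may mean to score the seven days of Week 26, whose diary is handed in at FU2. Protocol 7.9.3 leaves the detailed analysis of exploratory endpoints to the SAP, which postdates protocol V4.0, and the SAP does give a reason. This makes a deliberate choice plausible. It still departs from two protocol footnotes without saying so, and the reason explains when data are collected, not why the later week should count.

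Other points carry some weight:

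- **The SAP days are inferred.** The diary and CRF layout is not in the documents. This stands as a limit on the exact days. The textual conflict between looking back from FU1 and reading from FU2 does not depend on it.
- **The 4-of-7 rule may be meant for baseline only.** It directly follows the baseline definition, and SAP 4.4.5 pairs the two for baseline. On that reading the section is less at odds with itself, but the SAP then has no stated completeness rule for Week 26, whereas the protocol footnotes have one.
- **The missed-FU1 case is hypothetical.** It shows that the wording is not tied to dates; it is not an expected pattern.
- **SAP 4.1.4 already handles early stoppers.** It maps visits to weeks, but that mapping is what makes FU2 the wrong label in 4.7.3.
- **The shift is short.** With a half-life of about 25 days (Protocol 5.2.3.4) and simple mono-exponential decline, serum concentration falls by 1 − 2^(−7/25), about 18%, over 7 days. This supports calling the consequence small. It does not show that the itch scores would agree.

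**Conclusion.** The concern holds. The SAP's Week 26 PP-NRS rule contradicts the protocol's scoring rule for the same endpoint. With FU1 attended, the SAP window falls 7 or 8 days after the protocol window and shares no day with it, or 6 days after with one shared day if the visit day counts in both. If FU1 was missed, the same words could point 6 or 7 days too early.

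These figures assume that the FU2 record starts at the previous attended visit, as the SAP's collection sentence implies. The size and direction of any bias in the itch result cannot be computed, because the documents give no PP-NRS time course.

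The endpoint is exploratory and SAP 4.1.1 plans no hypothesis testing, so the consequence is small. It should still be corrected, because it changes the days behind a reported result. Confidence is medium, limited by the missing diary layout.

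**What to change.** In SAP 4.7.3, replace the FU2 sentence. Define the Week 26 PP-NRS as the mean of the daily scores over the 7 days immediately before the Week 26 visit, calculated only when at least 4 of the 7 entries are present. State that this visit is FU1 for patients last dosed at Week 24 and, for patients who stop earlier, the follow-up visit that SAP 4.1.4 maps to Week 26. Select scores by diary date, whichever visit the diary was collected at.

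If the later week is intended, state it as a departure from footnote 11 of Table 1 and footnote 4 of Table 2, and justify the choice of week as well as the collection route.

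The cost is one SAP sentence and a date-based derivation. No new data are needed, since the diary is already completed daily, provided its entries are dated.
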